Methods: We will conduct a RCT of prostate cancer survivors at 4 VHA sites (Ann Arbor, Cleveland, Pittsburgh and St. Louis) who are 1-10 years post-treatment. Those with clinically meaningful symptom burden identified using an established measure of prostate cancer symptom burden will be invited to the study, verbally consented and randomized to the automated telephone system or enhanced usual care (information about self-management). We will evaluate the impact of the intervention on confidence in symptom self-management as well as actual symptom burden and prostate cancer quality of life 5- and 12-months following enrollment. We will evaluate utilization of services 9-12 months post-enrollment using medical record/CPRS data sources. Finally, we will conduct a small process evaluation that will help us to better understand which elements of the intervention were effective, and will work with our primary care partners to make a recommendation for a broader deployment of an automated symptom self-management program in the VHA.

Our study will provide much needed information about how to optimize the quality of care and quality of life of Veterans who are survivors of prostate cancer. The randomized trial will evaluate innovative information for assessing and improving symptom burden and self-management of prostate-related symptom burden in these survivors. We will further understand how symptom burden is associated with use of appropriate services in the VHA. Finally, we will work with our primary care partners to inform how to improve survivorship care for this large and growing population of Veterans.

List of Abbreviations

Provide a list of all abbreviations used in the protocol and their associated meanings.

VA – Veterans Affairs

VHA – Veterans Health Administration

AE- Adverse Events

AAVA-Ann Arbor VA

CHCR – University of Michigan Center for Health Communications Research

CDW – Corporate Data Warehouse

CPRS – Computerized Patient Record System

EPIC – Expanded Prostate Cancer Index Composite

IVR- Interactive Voice Response

MTS- Michigan Tailoring System

PACT- Patient Aligned Care Team

PC – Prostate Cancer

PCP – Primary Care Physician

PEPPI -- Perceived Efficacy in Patient-Physician Interactions

PHI- Protected Health Information

QOL- Quality of Life

RCT – Randomized Controlled Trial

SAE – Serious Adverse Event

SAS- Statistical Analysis Software

SD- Standard Deviation

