The primary outcome for Specific Aim 2 will be use of VA services related to prostate cancer survivorship care at the 12 month assessment point. We will use the 12 month assessment point to ensure we capture any medication or service use related to prostate cancer symptom management that may occur after patients' exposure to the intervention has ended. Because there are no VA guidelines for appropriate management of prostate cancer survivors, we also will operationalize symptom-specific utilization consistent with MCC guidelines which are expert and evidence based. In the absence of VA guidelines for prostate cancer survivorship care, we considered national, regional and specialty organization guidelines. While there exists considerable overlap in recommendations, we ultimately chose the Michigan Cancer Consortium (MCC) guidelines for prostate cancer survivorship care as a standard against which to assess self-management approaches as well as use of services. We chose the MCC guidelines because they have good coverage of symptom management, the consortium is based in the same geographic area as our study sites, and because 2 study co-investigators contributed to their content ([name], [name]). We will operationalize utilization consistent with these guidelines using criteria mapping. This process has been used extensively to develop sets of quality metrics using a set of recommendations, when evidence-based guidelines do not exist, as is the case with prostate cancer survivorship care. Specifically, for each symptom indicated by the participant at baseline, we will determine potentially appropriate use of services by mapping receipt of services at the 12 month assessment to those outlined in the MCC recommendations. For analysis purposes, we will consider care recommended by the MCC as "guideline-concordant" even though the MCC are not fully evidence based guidelines. Data will be derived from three sources described in the Analytic Plan section below. For instance, if the patient indicates a problem with sexual function at baseline, we will measure use of pharmacologic treatments such as the phosphodiesterase inhibitors (sildenafil, tadalafil, vardenafil) or prostaglandin E1 (alprostadil as injection or intraurethral pellet), use of medical devices such as a vacuum erection device, a visit to a urologist, or receipt of surgery such as a penile prosthesis. Pharmacological agents for managing problems with urination include oxybutynin (Ditropan), tolterodine (Detrol) and phenazopyridine. Global measures for each symptom will indicate use of any of the pharmacologic, device, or referral measures suggested in the guideline. We also will create continuous measures of guideline-concordance service use from zero (none of the non-self-management approaches used in the prior year) to the maximum number of options for that specific symptom. Switching from one pharmacologic approach to another will be counted as separate approaches. The outcomes for Aim 2 (use of prostate cancer survivorship services consistent with those recommended by the MCC) will be obtained from two sources. We will collect pharmacy data, patient demographics, diagnoses, the date and type of utilization events, location of services (study site as well as clinic type), and the patients' assigned primary care provider from the Corporate Data Warehouse (CDW). To obtain information about device utilization, such as a penile clamp for incontinence control, we will use both CDW and the National Patient Prosthetics Database (NPPD) from Patient Care Services. Having the CDW and the NPPD records will ensure we can collect the most accurate device utilization. The process for requesting a data extract from these sources will be initiated at the end of year 2, to ensure sufficient time to obtain appropriate approvals for these datasets to be accessed by the data analyst from the AAVAHS.

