
We will collect information about participants' use of primary and specialty care from VA records in the 12 months between study enrollment and the final assessment. To account for services potentially received outside of the VA, we will ask participants at both the 5- and 12-month assessments to report the number of times over the prior interval that they visited their VA primary care physician and a specialist (urologist, oncologist, radiation oncologist, or gastroenterologist). For each visit, we will ask them to indicate whether the visit was related to their prostate cancer symptom management. We will also use the datasets created through Aim 2 to assess patients' use of primary and/or specialty care 12-months post enrollment.

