Aim 2 Analysis: For Aim 2, we hypothesize that 12 months after enrollment, Veterans in the automated prostate cancer symptom management intervention will have higher rates of use for PC survivorship services that are consistent with the recommendations of the MCC than control patients. The primary outcome for Specific Aim 2 will be use of symptom-specific MCC guideline-concordant care assessed at 12 months. Using our global measure of use of any symptom-specific guideline concordant care (yes/no), we will evaluate differences across intervention conditions

using a logistic regression model including all participants and controlling for potential baseline confounders. We will then conduct additional logistic analysis within subgroups of patients with various symptom patterns at baseline. For these models, the primary outcome will be use of guideline-concordant care for a specific symptom (yes/no). Secondary independent variables will include the EPIC baseline score. We will control for Veteran demographics (including age, race/ethnicity, education and income), study site, and type of treatment received (i.e., radiation versus chemotherapy). We will then explore the total amount of guideline concordant services received in regression models appropriate for skewed count data (e.g., poisson or negative binomial models).

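### The Aim 2 service-use outcome is modelled without pre-enrolment use as a named covariate, and no look-back is specified; the comparison stays valid but may lose precision.

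*Combined protocol and SAP*

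**What the plan says.** Section 5.6 (Aim 2 Analysis) states: "The primary outcome for Specific Aim 2 will be use of symptom-specific MCC guideline-concordant care assessed at 12 months". Section 5.5 defines the coding: "Global measures for each symptom will indicate use of any of the pharmacologic, device, or referral measures suggested in the guideline". Baseline contributes the symptom to be mapped, not the services already in use: "for each symptom indicated by the participant at baseline, we will determine potentially appropriate use of services by mapping receipt of services", with receipt of services taken at the 12-month assessment. A second, continuous measure runs "from zero (none of the non-self-management approaches used in the prior year) to the maximum number of options for that specific symptom", and a switch between drugs counts as a separate approach.

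Section 5.5 takes records of "use of primary and specialty care from VA records in the 12 months between study enrollment and the final assessment". The Abstract gives another window: "We will evaluate utilization of services 9-12 months post-enrollment using medical record/CPRS data sources".

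The primary comparison is made "using a logistic regression model including all participants and controlling for potential baseline confounders". After introducing models within symptom subgroups, section 5.6 adds the baseline EPIC score as a secondary independent variable and says: "We will control for Veteran demographics (including age, race/ethnicity, education and income), study site, and type of treatment received". Service use before enrolment is not named in either place. Section 5.4 admits men 1 to 10 years after treatment and does not exclude those already receiving the listed care. Section 5.5 collects dated utilisation events from the Corporate Data Warehouse (CDW) and device data from the CDW and the National Patient Prosthetics Database (NPPD), but asks for no period before enrolment.

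**The concern.** Several listed measures recur: oral drugs for erectile or urinary problems, and urology visits. A man who took one of these before enrolment and simply carries on scores yes in whichever arm he falls. Past use of a service is usually a strong predictor of later use, so leaving it out of the model leaves explainable variation in the comparison and gives no protection against a chance imbalance in prior users.

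Aim 1 is treated differently. Its sample size depends on adjusting for the baseline value of the outcome. Aim 2 has no such adjustment and no power calculation. A real rise in guideline-concordant care could be missed, and the reported rates would mix continuing with newly started care.

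**Working it through.** **The plan's own figure (Aim 1).** Inputs from section 5.6: difference 0.33 SD, α 0.0125 (taken as two-sided), power 90%, baseline-follow-up correlation 0.5. For analysis of covariance, n per group = 2(z₁₋α/₂ + z₁₋β)²(1 − ρ²)/δ² = 2 × (2.498 + 1.282)² × 0.75/0.33² ≈ 197, or 394 in total, as stated. Attrition also reproduces: 550 × 0.85² = 397. Without the baseline adjustment the same formula gives 263 per group, so the plan already relies on this kind of gain for Aim 1.

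**Aim 2.** The documents give no rates, effect size or share of prior users, so everything below is an assumption shown over a range:
- 275 per arm (550/2, records available for all), two-sided α 0.05
- new use among men without prior use: 20% control v 32% intervention
- share of prior users q = 20%, 40%, 60%
- continuation among prior users, s: 90% in both arms; 60% in both arms; or 60% control v 72% intervention

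The outcome rate in each arm is p = q·s + (1 − q)·(new-use rate). Power without the covariate is approximately Φ(Δ/SE − 1.96), with SE = √{[p₁(1 − p₁) + p₂(1 − p₂)]/275}.

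Worked at q = 40%:
- s = 90% in both: p₁ = 0.36 + 0.12 = 0.480, p₂ = 0.36 + 0.192 = 0.552, Δ = 0.072, SE = 0.0425, power = Φ(−0.27) ≈ 39%.
- s = 60% in both: p₁ = 0.24 + 0.12 = 0.360, p₂ = 0.24 + 0.192 = 0.432, Δ = 0.072, SE = 0.0416, power = Φ(−0.23) ≈ 41%.
- s = 60% v 72%: p₁ = 0.360, p₂ = 0.288 + 0.192 = 0.480, Δ = 0.120, SE = 0.0418, power = Φ(0.91) ≈ 82%.

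Power with the covariate comes from simulated logistic regressions of 1,000 to 1,500 runs per cell (simulation standard error at most √(0.25/1000) = 1.6 points; ranges show repeated runs). For q = 20/40/60%:

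| Continuation in prior users | As planned, % | Adjusted for prior use, % | Men without prior use only, % |
|---|---|---|---|
| 90% in both arms | 62-64 / 38-41 / 19-22 | 77-79 / 57-60 / 33-35 | 81-82 / 70 / 50-52 |
| 60% in both arms | 69 / 41 / 21-22 | 70-71 / 43-44 / 21-23 | as above |
| 60% v 72% | 83-84 / 81-82 / 80 | 87-88 / 86-87 / 84-86 | 81 / 70 / 50 |

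An intermediate case, 70% continuation in both arms at q = 40%, goes from 42% to 48% with adjustment.

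**Reading the table.** With no effect in prior users, Δ shrinks to (1 − q) × 12 points: 9.6, 7.2 and 4.8. That dilution drives most of the fall in power, and a covariate cannot undo it. What the covariate recovers depends on how well prior use predicts later use: substantial at 90% continuation, little at 60%. If prior users also respond, Δ stays at 12 points and the fall largely disappears.

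**The case against.** Four stronger readings are tempting, and the documents do not support them.

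**That the plan rules out adjustment for prior use.** It does not. The primary model's list of baseline confounders is open, and the named demographics, site and treatment follow the subgroup models, so they are not clearly the full set for the primary model. Nor can one say that a screen would leave prior use out. Section 5.6 describes no screen for Aim 2, and the Aim 1 data-verification text looks at covariate-outcome as well as covariate-group associations. What stands is that prior use is not named and no data are specified from which to derive it.

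**That the result would be biased.** Prior users are balanced in expectation by randomisation. The cost is precision and exposure to chance imbalance.

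**That existing users are fixed at yes.** Some will stop, and retaining or returning them to care is a legitimate success: section 3.0 hypothesises a higher rate of symptom-specific use, not of new use. The count measure can register drug switching. A device or operation obtained once before enrolment would not be recorded again in the window. The issue is confined to recurring use.

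**That power must collapse.** A fall to around 20% needs 60% prior users and no effect among them. If the intervention also moves prior users by 12 points, power as planned stays near 80% or above, and the analysis restricted to men without prior use is then the weakest of the three.

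It is also fair to say that records-based prior use is imperfect, because earlier non-VA care would not appear in it.

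**Conclusion.** The point holds as an inexpensive improvement in precision, not as an error of validity. The Aim 2 outcome is any guideline-concordant use after enrolment, in men who may already be using such care, and neither a prior-use covariate nor a look-back is specified.

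The gain is unknown. Under the assumptions shown it is roughly 11 to 19 percentage points of power when 90% of prior users continue in both arms, 0 to 3 points when 60% continue in both, and about 3 to 6 points when the intervention also raises continuation from 60% to 72%. Adjustment did not lose power in any scenario tried. All of these figures rest on assumed rates, not on anything in the documents.

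**What to change.** 1. Extend the CDW and NPPD extract to 12 months before enrolment. Code the same yes/no measure and the same count for that period.
2. Prespecify them as fixed covariates: the yes/no measure in the Aim 2 logistic models, the count in the Poisson or negative binomial models. Name them in section 5.6 so that inclusion does not depend on how the confounder wording is read.
3. Keep any use as the primary outcome, since that is what the hypothesis addresses. Report new use among men without prior VA use as a prespecified supporting analysis only.
4. Reconcile the outcome window between the Abstract (9-12 months) and section 5.5 (12 months from enrolment), so that the look-back matches it. The prior-use issue arises under either window.

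The cost is an earlier start date in a data request that section 5.5 schedules for the end of year 2, some extra data handling, and an additional covariate per model. No patient contact is needed. Men whose earlier care was outside the VA will be misclassified as having no prior use. This weakens the covariate and should be acknowledged when the supporting analysis is reported.

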5.6 Data Analysis

- **Provide sample size determination and analysis (include anticipated rate of screen failures, study discontinuations, lost to follow-up etc.).**

In a recent EPIC study, the minimal clinically important difference for the four EPIC domains was defined as the difference in scores between patients who were completely satisfied with their symptom burden (function and bother combined) versus only somewhat satisfied. Minimally important differences ranged from 0.33 standard deviation (SD) to 0.5 SD, which translated into a difference of six points for urinary incontinence scores, four points for bowel, 10 points for sexual function, and 4 points for hormonal symptoms. In the proposed study, we consider these differences as the clinically meaningful between-group mean difference in symptom reduction. To detect a 0.33 SD difference in symptom reduction between patients receiving the automated PC symptom support versus standard information at 12

month with 90% power, we will need 394 participants (197 per group), based on using a regression analysis adjusting for baseline values (analysis of covariance) with an α of 0.0125 with 0.5 as an assumed correlation between baseline and follow-up symptom scores. Note that the α value was chosen conservatively to detect symptom reduction in any of the four domains. The power will be higher to detect a larger than 0.33 SD between-group difference in symptom reduction and also to detect the same difference with higher correlation than 0.5 between baseline and follow-up symptom values. Assuming conservatively 15% attrition at each assessment time, we propose to enroll 550 participants in total with an anticipated 397 participants to complete assessments at the second assessment time. The number of eligible prostate cancer patients at each site is sufficient for recruitment. For interval scale outcomes measures such as confidence in symptom self-management, the proposed sample size should give adequate power to detect at least 0.33 SD differences between groups.

- **Describe how, where and by whom the data will be analyzed.**

All data will be analyzed at the Ann Arbor VA. The qualitative data analyst, [name], the data manager, [name], and Drs. [name], [name] and [name] will participate in the data analysis.

Aim 1 initial analyses and data verification: Analyses will be done in three phases. Baseline analysis (data verification) will include examining the distribution of all study variables to assess extreme values, missing data, variances, skewness, and type of distribution. Descriptive statistics will be used to describe the distribution of baseline variables in the two groups. We will use means, medians, and ranges for continuous variables such as age and baseline symptom scores, and we will use proportions for discrete variables. Baseline comparability of the two groups will be assessed using two-group t-tests for continuous variables, and chi-square tests for dichotomous or categorical variables. Variables found to be associated with the study groups will be included in subsequent analyses as covariates to adjust for potential differences between groups, and the results will be interpreted with any baseline imbalances in mind. We also will evaluate bivariate associations between patients' experimental condition and the outcomes, as well as between each covariate and the outcomes and between each covariate and group assignment. These analyses will be done to determine unadjusted measures of effect, assess possible confounders, and anticipate any collinearity in subsequent analyses. We will also report by study group the percent of patients who reached EPIC symptom scores above 70 (i.e., "better symptom burden") at both 5- and 12- months. In the final phase we will use multivariable models to estimate the intervention effect. We will conduct graphical analysis to explore variation in outcome variables over time and between the two experimental groups. We will evaluate the trends in symptom burden, knowledge and information need over time in the two study groups separately. Results of these graphical analyses will be used to fine-tune the analytic course described below.

Aim 1 outcome analyses: Our primary outcomes for Aim 1 will be changes in symptom burden and bother scores at 5-months relative to baseline, using the EPIC measure. We will also evaluate these outcomes at the 12-month assessment point, but focus on the 5-month for primary outcome assessment as it is closest to the completion of the intervention. Multiple regression analysis will be used to evaluate the primary outcomes. The model will include an indicator for intervention group as the primary independent variable, and treatment type indicator (surgery vs. radiotherapy) and study site indicators as covariates. Baseline variables found to differ between the two study groups in the baseline analysis will also be included as covariates, though we expect the groups to be balanced on demographic and symptom scores by the randomization process. The coefficient for the intervention group indicator will be used to evaluate the impact of the personalized automated prostate cancer symptom management program compared to standard information. For change in symptom burden, we will repeat the analysis using each of the four symptom domains for EPIC. We will use the same analytic approach to evaluate changes in confidence in symptom self-management, our second Aim 1 outcome. We hypothesize that for both Aim 1 outcomes, intervention group survivors will have better scores at both 5- and 12-month assessments relative to those in the group (i.e., less symptom burden and better PC-QOL, more confidence in symptom self-management). For patients with available data at both 5- and 12-months, we will assess the trajectory of symptoms over time. This will be done using a linear mixed-effects model with random effects for each subject, an indicator for intervention group, an indicator of follow-up wave (5 versus 12 months) and an interaction of time by intervention group to model potential changes in the intervention effect on symptoms soon (at 5-months) vs. long (at 12-months) after the intervention is discontinued. If the interaction is not significant, we will drop the interaction term from the model and estimate the time-averaged difference in outcomes between the two study groups. Analyses of other outcomes, such as self-management implementation and confidence, will be done similarly.

Aim 2 Analysis: For Aim 2, we hypothesize that 12 months after enrollment, Veterans in the automated prostate cancer symptom management intervention will have higher rates of use for PC survivorship services that are consistent with the recommendations of the MCC than control patients. The primary outcome for Specific Aim 2 will be use of symptom-specific MCC guideline-concordant care assessed at 12 months. Using our global measure of use of any symptom-specific guideline concordant care (yes/no), we will evaluate differences across intervention conditions

using a logistic regression model including all participants and controlling for potential baseline confounders. We will then conduct additional logistic analysis within subgroups of patients with various symptom patterns at baseline. For these models, the primary outcome will be use of guideline-concordant care for a specific symptom (yes/no). Secondary independent variables will include the EPIC baseline score. We will control for Veteran demographics (including age, race/ethnicity, education and income), study site, and type of treatment received (i.e., radiation versus chemotherapy). We will then explore the total amount of guideline concordant services received in regression models appropriate for skewed count data (e.g., poisson or negative binomial models).

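### The trial is sized at α = 0.0125 for four EPIC domains, but the analysis section gives no multiplicity rule; naming Holm would fill the gap with more power than a fixed 0.0125

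*Combined protocol and SAP*

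**What the plan says.** The sample size paragraph of section 5.6 plans "To detect a 0.33 SD difference in symptom reduction" with 90% power, "with an α of 0.0125" and "0.5 as an assumed correlation between baseline and follow-up symptom scores", and arrives at "394 participants (197 per group"). The choice of α is explained in one sentence: "Note that the α value was chosen conservatively to detect symptom reduction in any of the four domains". With 15% attrition at each assessment, 550 enrolled leave 397 at the second follow-up.

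The Aim 1 outcome analyses, also in section 5.6, describe the regression and then say: "For change in symptom burden, we will repeat the analysis using each of the four symptom domains for EPIC". No threshold, family-wise level or multiplicity procedure is attached to these four tests. The 0.0125 appears only as a sample size input, and the overall 0.05 is not written anywhere.

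**The concern.** Four tests of the primary measure have no stated decision rule. An analyst could carry over the planning value and test each domain at 0.0125, or could test each at 0.05 with no control across domains. The plan does not settle which before the data are seen.

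The only rule the text implies is a fixed 0.0125 in each domain. That is valid but not the most efficient choice. Holm compares the smallest p-value with 0.05/4 = 0.0125, the next with 0.05/3 = 0.0167, the next with 0.05/2 = 0.025 and the largest with 0.05, stopping at the first failure. It holds the family-wise error at 0.05 under any dependence between the domains and rejects everything that a fixed 0.0125 rejects. At stake is the power to show second and later domains. This matters because the plan gives each domain its own clinically important difference and analyses each one separately.

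**Working it through.** **Inputs from section 5.6:** 0.33 SD; α = 0.0125; power 90%; baseline to follow-up correlation 0.5; equal groups; 550 enrolled; 15% attrition at each of two assessments.

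**Assumed:** two-sided testing; overall level 0.05 (4 × 0.0125 = 0.05); equal correlation between the four domain test statistics of 0 to 0.5, because the documents give none.

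**1. The plan's own figure.** The ANCOVA residual variance is 1 − 0.5² = 0.75. Then n per group = 2 × (2.498 + 1.282)² × 0.75 / 0.33² = 196.7, so 197 per group and 394 in total. This matches the plan exactly. A one-sided test gives 342, so the two-sided reading is the one that fits. Completers: 550 × 0.85² = 397, which also matches.

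**2. Power in one domain at fixed 0.0125, 397 completers.** The expected z is 0.33 / (0.866 × √(4/397)) = 3.796. Power = Φ(3.796 − 2.498) = 90.3%.

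**3. Fixed 0.0125 against Holm.** Four correlated normal test statistics were simulated with 397 completers and a true effect of 0.33 SD in each responding domain.

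| Domains that respond | Per-domain power, fixed 0.0125 | Per-domain power, Holm |
|---|---|---|
| 4 | 90% | 95-96% |
| 3 | 90% | 93-94% |
| 2 | 90% | about 92% |
| 1 | 90% | about 0.1 point higher |

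If all four respond, the chance of showing all four rises from 67-75% to 87-89%. As a check on the lower end, independent tests at fixed 0.0125 give 0.903⁴ = 0.665, or about 67%.

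**4. Sensitivity, all four domains responding.**
- Correlation 0.7 with 394 patients: per-domain power 90.0% to 94.3%; all four shown 78.4% to 90.3%.
- 5-month assessment (550 × 0.85 = 467.5, taken as 467): per-domain 95% to 97-98%; all four shown 81-85% to 94-95%.
- True effect 0.25 SD with 397 completers: per-domain 65% to 74-76%.

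**5. What stays the same.** Holm's first threshold is 0.0125, so it rejects at least one domain exactly when a fixed 0.0125 does. With all four effects real and 394 patients, that chance is 99.99%, 99.7% and 99.1% under either rule at correlations 0, 0.3 and 0.5. The required 394 is unchanged for the same reason.

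**6. Error control.** The simulated family-wise error under Holm was at most 0.0491 in every scenario. With no true effect in any domain it equals that of a fixed 0.0125.

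**The case against.** The strongest case against is that this criticises a rule the plan does not state. A reader might infer that the protocol commits to testing each domain at 0.0125. It does not: the figure is a planning value, and the analysis text is silent. That stands, and it is why the point is the missing rule first and the more efficient choice second.

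It is also fair that the stated aim of the 0.0125 is to find an effect in any of the four domains, and for that aim Holm adds nothing when all four respond. The gain is in domain-by-domain conclusions, and it shrinks quickly as fewer domains respond. A uniform effect is far from assured: eligibility needs a qualifying score on only one symptom, and intervention patients choose what to work on. The all-four figures are therefore the favourable end. What survives is that Holm is never worse and that the plan does test each domain.

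Two further readings should be resisted.
- A reader might take 90% as the minimum per-domain power. It holds only at 0.33 SD with baseline-adjusted ANCOVA. The Aim 1 text analyses change scores and adds baseline variables only if the groups differ on them. Read literally, at correlation 0.5 the SD of change is √(2 × (1 − 0.5)) = 1, z is 0.33 / √(4/397) = 3.288, and power at 0.0125 is Φ(3.288 − 2.498) = about 79%.
- A reader might think that Holm over four tests settles multiplicity. Section 5.1 names three primary outcomes at two time points, and section 5.6 sizes the trial at 12 months while making 5 months primary. The four-domain rule covers none of the additional tests and does not resolve that conflict.

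**Conclusion.** The point holds as an improvement, not as an error in the plan. The analysis section lacks a multiplicity rule for the four EPIC domains. The rule implied by the sample size would be valid, but Holm gives the same family-wise control and never less power. At 397 completers the per-domain gain is about 5 to 6 points if all four domains respond, 3 to 4 if three do, under 2 if two do and about 0.1 if one does. These sizes rest on the plan's ANCOVA inputs, on two-sided testing at an overall 0.05 (inferred, but consistent with 394) and on an assumed between-domain correlation of 0 to 0.5. That Holm is valid and at least as powerful does not depend on that correlation.

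**What to change.** Add to the Aim 1 outcome analyses in section 5.6 a statement that the four EPIC domain comparisons at the declared primary time point are tested with the Holm step-down procedure at a two-sided family-wise level of 0.05 (ordered thresholds 0.0125, 0.0167, 0.025 and 0.05). Leave the sample size as it is.

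Add that decisions rest on the Holm-adjusted p-values. If 98.75% intervals are reported, one may include zero for a domain that Holm declares positive (p between 0.0125 and its Holm threshold), and readers should be told so. That possible mismatch is the only cost beyond wording; no extra patients or data are needed. The sentence should be fixed before the outcome data are analysed. It covers the four domain tests only: the other outcomes and the second time point need their own statement.
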